### **Recruitment:**

We recruited 20 sites (14 in Ontario and 6 in British Columbia, Canada). Site recruitment focused primarily on the engagement of contacted sites to reduce the risk of site withdrawl. For patient participant recruitment, staff at each primary care site screened patients for their willingness to participate when they called to book an appointment. If patients booked online, their reason for visit was screened by the clinic staff and staff reached out to potential participants for their willingness to be contacted by a research assistant. Trained research assistants screened potential participants using inclusion/exclusion criteria and enrolled consenting patients. Patients who raised LBP with any provider during a clinical encounter were also identified as potential participants. In these cases, they were directed to the administrative team, who then connected them with a research assistant for screening and enrollment. Balance in recruitment across arms and across clusters was monitored throughout the study and strategies were implemented to maintain consistent implementation of recruitment processes across sites.

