### **Sample Size and Power Calculations:**

We used the methodology of Teerenstra et al. to calculate the required number of clusters based on an ANCOVA analysis for the primary outcome (Roland-Morris Disability Questionnaire [RMDQ]) at 12 months adjusting for baseline. Our target sample was 20 clusters (10 per arm) allowing for 1560 patient participants (78 per practice before attrition). Conservatively accounting for attrition of two clusters (resulting in 18 clusters) and 20% of patients (resulting in 63 patients/cluster), this target would achieve 90% power to detect a minimally important mean difference of 2.5 points (Cohen's  $d=0.4$ ) using a two-sided  $\alpha=0.05$  and assuming a standard deviation (SD) of 5.7 points based on pilot study data, a conservative intracluster correlation coefficient of 0.1, a cluster autocorrelation coefficient (correlation between cluster means at baseline and follow-up) of 0.5, and an individual autocorrelation coefficient (correlation between participant scores at baseline and follow-up) of 0.6 informed by our pilot study. An average rate of 1.5 patient participants per site each week over one year would achieve the recruitment target of 1560 participants, which we anticipated based on our pilot study where we recruited and retained four sites and achieved a recruitment rate of >1.7 participants/site/week. Recruitment of 400 patient participants across 18 clusters (22 participants/cluster) would achieve 80% power.

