#### **Patient health and experience outcomes**

For our patient health outcomes, we will use linear mixed models to estimate individual patient participant outcomes adjusting for clustering by primary care centre. Our primary outcome (RMDQ) with repeated measures at baseline and the 6-week, 3-, 6-, 9-, and 12-month follow-up time points will be analyzed using linear mixed regression (using *PROC MIXED* in SAS), estimated using restricted

maximum likelihood (REML) estimation and a Kenward-Rogers degrees of freedom correction to account for a small number of clusters. The model will include fixed effects for time, intervention group by time interaction, (omitting the group main effect to ensure baseline differences are constrained to zero), factors used in the covariate-constrained allocation procedure (rurality of the cluster, number of active patients) and other pre-specified covariates associated with LBP-related disability (patient participant age, sex, income, highest level of education achieved, duration of current episode of LBP, Functional Comorbidity Index score). The correlation in repeated measures on the same participant will be modeled using a suitable covariance structure, identified using information criteria (AIC/BIC). To account for clustering within practices, site will be modeled as a random effect. The intervention effect will be obtained as the adjusted least square mean difference between arms at 12 months, with 95% confidence intervals. Secondary comparisons will be obtained using least square mean differences at intermediate time points.

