Pain intensity, health-related quality of life (EQ-5D-5L), PSEQ, PCS, TSK-11, and PHQ-2 outcomes will be analyzed as described for the primary outcome, adjusted for the same covariates. Patient satisfaction and global rating of change outcomes have no baseline measures, and will be analyzed using ordinal logistic regression with clusters as random effects, adjusting for the same covariates as described above. When individual items are missing from within any of the questionnaires, we will use simple mean imputation as suggested by Chavance. Serious adverse events will be presented descriptively by arm due to low expected counts. Any adverse events (yes/no) will be presented as incidence rates with confidence intervals and compared by calculating relative risks with confidence intervals from robust Poisson regression using GEE-type robust variance estimators (using *PROC GLIMMIX* with *EMPIRICAL* option in SAS) to account for clustering and using an exchangeable working correlation matrix. We will use empirical covariance (“sandwich”) bias-adjusted (residual-based) estimators and the Fay and Graubard correction to account for small number of clusters in all models comparing incidence rates. In the case of non-convergence or unstable estimates due to the small number of clusters, we would attempt to fit the model using an independent working correlation matrix. Other information related to non-serious adverse events (i.e., severity and duration) will be reported descriptively.

We have planned a secondary analysis, a responder analysis, to compare the proportion of participants who experience a meaningful improvement in disability (RMDQ) in the PT-led primary care model arm versus the usual care arm. We will define a meaningful improvement as an improvement of greater than or equal to 30% improvement on the RMDQ, corresponding to an established minimally important difference among people with LBP. We will calculate the proportion of participants who

experience a meaningful improvement in each arm and compare between groups using robust Poisson regression, with GEE-type robust variance estimators to account for clustering. We will use empirical covariance (“sandwich”) bias-adjusted (residual-based) estimators and the Fay and Graubard correction to account for small number of clusters.

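### The primary mixed model states no site-level covariance over time; read as a site random intercept, it makes the 12-month confidence interval too narrow whenever site effects shift during the year

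*Combined protocol and SAP*

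**What the plan says.** Under Patient health and experience outcomes, the primary analysis is a REML linear mixed model of RMDQ at baseline and five follow-ups with Kenward-Roger degrees of freedom. It has no group main effect, so the arms share a baseline mean and the 12-month effect is a group-by-time term. Two sentences define the covariance. For participants: "The correlation in repeated measures on the same participant will be modeled using a suitable covariance structure, identified using information criteria (AIC/BIC". For sites: "To account for clustering within practices, site will be modeled as a random effect". No site-by-time term and no site-level covariance over time is stated.

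The same section reserves its cluster-robust, small-sample variance for other models. It applies "the Fay and Graubard correction to account for small number of clusters in all models comparing incidence rates", and also to the responder analysis, but not to the linear mixed model.

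Sample Size and Power Calculations sizes the trial "based on an ANCOVA analysis for the primary outcome (Roland-Morris Disability Questionnaire [RMDQ]) at 12 months adjusting for baseline". It uses "a conservative intracluster correlation coefficient of 0.1" and "a cluster autocorrelation coefficient (correlation between cluster means at baseline and follow-up) of 0.5".

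**The concern.** A site random intercept is one deviation per site, identical at every visit. Planning on an autocorrelation of 0.5 says the opposite: much of a site's deviation at 12 months was not there at baseline.

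The mismatch affects the primary contrast directly. With the baseline difference constrained to zero, the model uses the other visits to remove what it takes to be a permanent site effect. Any site-by-visit variation is then left in the estimate but not in its standard error. Kenward-Roger adjusts for having estimated the components in the model; it does not add a missing one. In simulation at 18 sites of 63, the median Satterthwaite df for the 12-month contrast was about 3,700, so the test behaves almost as if patients were independent.

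At stake are the primary confidence interval and p-value. The mediation analyses depend on them too, because they run only if the treatment effect is significant and take their total effect from the same model. Pain, EQ-5D-5L, PSEQ, PCS, TSK-11 and PHQ-2 use the same model and carry the same risk. Its size for those outcomes cannot be given, because no ICC or autocorrelation is stated for them.

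**Working it through.** **Inputs** (Sample Size and Power Calculations): SD 5.7, difference 2.5, two-sided alpha 0.05, ICC 0.1, cluster autocorrelation (CAC) 0.5, individual autocorrelation (IAC) 0.6. Scenarios are 18 sites of m = 63 and 18 sites of m = 22.

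**1. The plan's own figure.** For cluster ANCOVA:

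- r = [m·ICC·CAC + (1−ICC)·IAC] / [1+(m−1)·ICC] = (3.15 + 0.54)/7.2 = 0.5125
- design effect = 7.2 × (1 − 0.5125²) = 5.31
- SE = 5.7 × √[2 × 5.31/(9 × 63)] = 0.780
- power = Φ(2.5/0.780 − 1.96) = 89.3%, or 85.3% on 16 df

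The stated 90% is reproduced on the normal reference. At m = 22 the SE is 0.856, with power 83.2% (normal) or 78.3% (16 df), against this statement: "Recruitment of 400 patient participants across 18 clusters (22 participants/cluster) would achieve 80% power".

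**2. Hand check of the site-intercept model.** Take two visits and work in units of SD². A site mean truly has variance v = 0.1 + 0.9/63 = 0.1143, and covariance between visits c = 0.05 + 0.54/63 = 0.0586. Assume the fitted site variance settles at the between-visit site covariance, ICC × CAC = 0.05. Then:

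- variance the model sees: 0.05 + 0.9/63 = 0.0643
- baseline slope it uses: b = 0.0586/0.0643 = 0.911 (the correct slope is 0.5125)
- SE it reports: 5.7 × √[(2/9) × 0.0643 × (1 − 0.911²)] = 0.281
- SE that estimator really has: 5.7 × √[(2/9) × (v(1 + b²) − 2bc)] = 0.860
- rejection under the null: 2 × [1 − Φ(1.96 × 0.281/0.860)] = 52%

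**3. Simulation.** Six visits (0, 6, 12, 26, 39, 52 weeks), null effect, constrained baseline, REML with all components estimated, exchangeable participant covariance, equal site sizes, no covariates, Satterthwaite df in place of Kenward-Roger. Assumption: the CAC applies equally between all pairs of visits. The plan defines it only between baseline and follow-up.

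| Sites × patients | ICC | CAC | Two-sided rejection, site intercept only |
|---|---|---|---|
| 18 × 63 | 0.1 | 0.5 | 48.7% (24.7% favour PT-led, 24.0% usual care) |
| 20 × 78 | 0.1 | 0.5 | 54.0% |
| 20 × 63 | 0.1 | 0.5 | 50.6% |
| 18 × 22 | 0.1 | 0.5 | 28.8% |
| 18 × 63 | 0.05 | 0.8 | 22.9% |
| 18 × 63 | 0.03 | 0.8 | 14.7% |
| 18 × 22 | 0.05 | 0.8 | 10.0% |
| 18 × 22 | 0.01 | 0.8 | 5.8% |
| CAC 1 (control) | – | 1.0 | 4.9% |

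The first row used 4,000 runs and the others 2,000. Monte Carlo error is 0.8-1.1 points near 50% and 0.5 near 5%. In the first row the mean model SE is 0.297 and the true SE 0.850. The interval half-width is therefore 1.96 × 0.297 = 0.58 points, where a correctly specified model at the planning SE has 1.96 × 0.780 = 1.53.

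Varying the setup at 18 × 63 (two or six visits, exchangeable or unstructured participant covariance, z or 16 df) gives 44-52%. With CAC 1, rejection returns to 6.1% (z) or 4.3% (16 df), so the omitted site-by-time variation is the cause.

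**4. Candidate remedies.** ICC 0.1, CAC 0.5, 18 sites, uneven site sizes (CV 0.4, assumed), 1,500 runs, no missing data. Rejection at 63 / 22 per site:

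| Site-level model | Equal site correlation | Correlation decaying to 0.5 at 12 months |
|---|---|---|
| Site + site-by-time | 6.9% / 6.4% | 13.9% / 10.9% |
| Spatial power | 6.1% / 5.6% | 5.3% / 5.7% |
| Chosen by AIC | 6.9% / 6.1% | 5.6% / 6.1% |

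A smaller repeat (200-300 runs per cell) put site-by-time alone at 8-11% under decay and spatial power at 5-6%. Under decay, the site-intercept model at 18 × 63 rejects 50.2%.

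**The case against.** The strongest reply is that the plan is silent, not wrong. It does not say intercept only, gives no random-effects code, and could be programmed with a site-by-time term. That is correct, and the finding is conditional on the natural reading. But two readings whose standard errors differ by more than a factor of two and a half (0.297 against 0.780) should not be left to a programmer's choice for a primary outcome.

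Second, the 49% sits near the top of a wide range. It needs the intercept reading, an ICC the plan calls conservative, an autocorrelation of 0.5 and 63 analysed per site. Planning values protect power and are not estimates. This also stands. Covariate adjustment, absent from the simulations, may lower the residual ICC as well. Milder inputs still give 10-23% in several cells.

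Third, one site-by-time effect restores the error rate when site correlation is equal across visits (4.9% on z, 3.5% on 16 df, with equal site sizes), and the documents nowhere mention decay. Choosing among structures with 18-20 sites adds a data-driven step, and the AIC choice still rejects 6.9% in one cell, above 5% by more than Monte Carlo error. The residual inflation is real but small. The plan already selects covariance this way at participant level, and correlation that fades over a year is plausible enough that site-by-time alone should not be presented as sufficient.

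Finally, the responder analysis does use a corrected cluster-robust variance. It is secondary and does not repair the primary interval.

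**Conclusion.** The concern holds and should be settled before analysis. The plan states no site-level covariance over time for its primary model, and its natural reading contradicts the autocorrelation on which the trial was sized. On that reading the 12-month interval is too narrow whenever site effects change during the year. At the planning inputs the two-sided type I error is about 49% (44-52% across variants), split evenly between the arms. It is about 29% at 22 per site, and 5-6% with ICC 0.01 and autocorrelation 0.8 at that size. If the true autocorrelation is 1 there is no inflation.

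These figures illustrate and do not forecast: the true ICC, true autocorrelation and achieved site size are not in the documents. They assume no covariates, complete data, and Satterthwaite, z or 16 df in place of exact Kenward-Roger df.

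**What to change.** Amend the primary model before analysis, by the route in Protocol and Analysis Plan Amendments.

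- State a site-level covariance over time that allows correlation below 1. Pre-specify two candidates: (i) site plus site-by-time random effects with categorical time; (ii) a decaying structure (AR(1), or spatial power over visit weeks). Choose by AIC/BIC. Keep the participant-level covariance, REML and Kenward-Roger.
- State a non-convergence fallback that does not revert to a site intercept alone, for example a 12-month ANCOVA with random site and individual baseline. Say that it gives up the intermediate visits on which the missing-at-random argument relies, so it is for non-convergence only. A site-mean baseline term is not needed for type I error and lowered power slightly.
- Apply the same to every outcome analysed like the primary one.

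**Cost.** A short amendment, a code change and a wider interval: SE about 0.78 at 63 per site and 0.86 at 22. Simulated power of the AIC-chosen model is 88% (18 × 63), 80-82% (18 × 22) and 92% (20 × 63), not corrected for its slight excess rejection. The fallback, simulated with 20% missing at 12 months, rejects 4.6-5.3% under the null, with power 84-85% at 63 per site and 76% at 22. The plan should acknowledge that power may fall slightly below its stated 90% and 80%, as the 16 df values above also show. Some site-level structures may not converge with 18-20 sites, which is why the fallback is needed.

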### **Health System and Societal Outcomes:**

Primary care physician or nurse practitioner encounters: the number of new and repeat primary care physician or nurse practitioner visits for LBP per patient. This measure will be considered a proxy for a potential increase in primary care team capacity achieved if the LBP-related workload of primary care physicians or nurse practitioners is reduced, thus increasing their availability to provide care to other patients.

Healthcare utilization within the primary care team: using data being collected from the EHR: consultations with other primary care team members (e.g., physicians, nurse practitioners, nurses, social workers, and occupational therapists) and group programming accessed within the primary care organization.

Healthcare utilization outside of the primary care team: using self-report data from follow-up surveys cross checked with reports the electronic health record when possible: medications used; walk-in clinic visits; ED visits; inpatient hospital stays; surgeries, injections, and other interventional procedures; visits to specialist physicians; diagnostic imaging; and visits to other health professionals outside the primary care team (e.g., chiropractors, massage therapists, occupational therapists, physiotherapists, chronic pain clinics).

Missed Occupational Activities: using self-report data from follow-up surveys: time (days) lost from paid employment, volunteer, homemaking, or educational activities related to LBP.

Assistance required: using self-report data from follow-up surveys: paid and unpaid assistance required. For example, self-care (e.g., taking medications, dressing/undressing, going to the bathroom, bathing/showering, grooming), shopping/groceries, meal preparation, housework, managing finances, or transportation (e.g., to a medical appointment).

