Costs: Total costs per person will be calculated by summing direct healthcare costs and indirect costs using a human capital approach for missed occupational activities. Sources of direct healthcare cost data: Intervention costs will include the PT salary and training needed to carry out the intervention. Costs for publicly funded healthcare services will be obtained from the Ontario Ministry of Health Schedule of Benefits. Medication costs will be obtained from the Ontario Drug Benefit formulary. Expenses related to health services funded by private insurance or out of pocket will be collected through self-report at all follow-up assessments. Other costs incurred by the participant related to their LBP are also being collected by self-report, including support or assistance for self-care, housework,

shopping, or transportation (e.g., to healthcare appointments). The total direct costs will be determined by multiplying the quantity of resource use by the corresponding unit cost, summing the total cost over each follow-up interval, and then calculating the mean cost at each follow-up time point, as well as an overall mean cost for the entire study period. *Indirect costs:* Non-healthcare costs will be limited to loss of productivity using a human capital approach. The mean provincial wage reported by Statistics Canada will be used to assign a monetary value to time lost from paid employment. The minimum wage value in Ontario and BC will be used to place a value on time lost by those who were retired and time lost from volunteer, homemaking, caregiving, or educational activities.

**Cost effectiveness:** We will conduct a cost-utility analysis from both societal (primary) and health payer (secondary) perspectives to meet the needs of all knowledge users. For both societal and health payer perspectives, we will estimate the incremental cost-per-QALY gained.

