### **Analysis**

#### **Effectiveness analysis**

All quantitative analyses will be conducted as per the Intention-To-Treat principle. Descriptive statistics for baseline characteristics and primary and secondary outcomes will be reported by arm using means (SD) or medians (interquartile range) for continuous variables and count (percent) for categorical variables. All analyses will be performed in SAS, version 9.4 (SAS Institute Inc; Cary, NC). Differences between arms will be compared, accounting for site clustering using linear mixed models and generalized estimating equations (GEE), and significance will be reported with p-values.

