The use of REML estimation under an assumption of Missing At Random (MAR) allows the use of all available data without the need for multiple imputation. To examine the risk of bias due to missing data, we will compare the characteristics of those remaining and those lost to follow-up to identify factors associated with attrition. We will perform a sensitivity analysis for a missing not at random (MNAR) departure from our MAR assumption using a delta-adjusted imputation pattern mixture model approach to investigate the robustness of our trial outcomes with regard to the missing values of the RMDQ. Within this sensitivity analysis approach, we will start with the posterior distributions suggested by an imputation model using multiple imputation by chained equation. Our imputation model will incorporate all variables in our primary analysis model, along with the last-observed-before-time covariates, and additional covariates needed for the pattern mixture. The sensitivity parameter (delta) will be introduced to explore how a departure from MAR affects results by specifying a maximum delta for each pattern of missing. We will set the maximum delta to be twice the residual sample standard deviation from the observed data fit of the primary linear mixed model. Our sensitivity analysis will use multiple imputation 9 times to generate estimated treatment effects for a range of sensitivity.

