#### Economic evaluation

We will estimate the cost-effectiveness of the PT-led care model from both a societal (primary) and health system payer (secondary) perspective to meet the needs of all knowledge users. The total costs will be determined by multiplying the quantity of resource use (or lost days) by the corresponding unit cost (or hourly wage), summing the total cost over each follow-up interval, and then calculating the mean cost at each follow-up time point, as well as an overall mean cost for the entire one-year study period. Results will be presented as aggregated and disaggregated costs. Utility data will be generated using EQ-5D-5L index values (ie. utility scores) from all follow-up assessment time points. We will estimate QALYs for every participant, using the area under the curve approach, assuming linear interpolation between the measurements. To accommodate the hierarchical structure of the data, we will use bivariate multilevel modeling to estimate the incremental cost-effectiveness ratio using a calculation of cost-per-QALY gained for PT-led primary care versus usual care and to estimate the incremental net benefit at various willingness to pay values. To account for clustering of study sites, as well as heterogeneity in costs and treatment effect across jurisdictions, we will model treatment group as

a fixed effect and the study site a random effect; adjusting for the same covariates as the primary analyses as fixed effects in our models. We will conduct a probabilistic sensitivity analysis using 10,000 Monte Carlo simulations to present the uncertainty in our cost-effectiveness estimates. Simulation results will be plotted on cost-effectiveness planes and we will generate cost-effectiveness acceptability curves to display the probability that the PT-led care model is cost-effective across a range of willingness to pay thresholds.

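### Are the responder and cost-utility results undermined because the stated missing-data provision covers only the linear mixed models?

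*Combined protocol and SAP*

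**What the plan says.** Under the analysis heading Patient health and experience outcomes, the RMDQ is analysed with a linear mixed model fitted by REML, which "allows the use of all available data without the need for multiple imputation". Pain, EQ-5D-5L as a health outcome, and the psychosocial scales follow the same model. A delta-adjusted pattern-mixture analysis, built on chained-equation imputation, tests departures from missing at random for the RMDQ. Single missing questionnaire items are mean-imputed.

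Three analyses or inputs lie outside that provision:

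- **Responder analysis** (same section): "We will define a meaningful improvement as an improvement of greater than or equal to 30% improvement on the RMDQ". It is fitted by robust Poisson regression, and nothing is said about participants without the score.
- **Economic evaluation**: "Utility data will be generated using EQ-5D-5L index values (ie. utility scores) from all follow-up assessment time points", and "We will estimate QALYs for every participant, using the area under the curve approach, assuming linear interpolation between the measurements". Costs are summed over follow-up intervals. Under Health System and Societal Outcomes, "Expenses related to health services funded by private insurance or out of pocket will be collected through self-report at all follow-up assessments", and utilization outside the team is obtained "using self-report data from follow-up surveys cross checked with reports the electronic health record when possible". For the joint analysis, "we will use bivariate multilevel modeling to estimate the incremental cost-effectiveness ratio".
- **Baseline covariates**: age, sex, income, education, episode duration and comorbidity score enter the adjusted models, with no rule for a missing value.

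The Effectiveness analysis section opens with a general statement: "All quantitative analyses will be conducted as per the Intention-To-Treat principle".

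**The concern.** A likelihood-based mixed model keeps a participant who drops out, using the visits that were observed. A one-value responder status, a person-level QALY and a person-level cost total do not have that property. Linear interpolation can bridge a gap between two visits but cannot supply a missing final value. An unreturned survey leaves a hole in a cost total. A record with a missing covariate is omitted by PROC MIXED whatever the estimator.

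If analysts simply ran each model on whoever had complete data, the responder and cost-utility results would rest on fewer people and a stronger missingness assumption than the primary result. That would sit awkwardly with the intention-to-treat statement. The trial is unblinded and only one arm gains a new provider, so dropout related to outcome differently by arm is possible. Cost-effectiveness is also one of the results that decision makers are meant to use.

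**Working it through.** **1. The plan's own figure.** Inputs from Sample Size and Power Calculations: 9 clusters per arm of 63 patients after attrition, SD 5.7, ICC 0.1, cluster autocorrelation 0.5, individual autocorrelation 0.6, difference 2.5, two-sided 0.05.

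- Design effect = 1 + 62 × 0.1 = 7.2
- r = (63 × 0.1 × 0.5 + 0.9 × 0.6) / 7.2 = 0.5125
- SE = √[2 × 5.7² / (9 × 63) × 7.2 × (1 − 0.5125²)] = 0.780
- Power (normal approximation) = Φ(2.5/0.780 − 1.96) = 0.893, against the stated 90%

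**2. How much could be missing.** Planned patient attrition is 0.20 × 1,560 = 312. If two clusters were also lost, 18 × 63 = 1,134 (72.7%) would remain. Suppose, as an assumption, that 2% or 5% of those retained miss each of the four earlier surveys. Complete self-reported costs are then 0.80 × 0.98⁴ = 74% or 0.80 × 0.95⁴ = 65%, and 67% or 59% with the cluster loss. Loss of clusters is a planning allowance; the document describes 20 participating sites.

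**3. Covariates.** Repeating step 1 with 10, 20 or 30% fewer patients per cluster gives power 0.890, 0.885 or 0.879. The documents do not give the actual amount missing.

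**4. Responder bias if complete cases were used.** SD 5.7 and baseline-to-follow-up correlation 0.6 come from the plan. Assumed: means 11 at baseline and 7.5 at months 9 and 12, 9-to-12-month correlation 0.6, 0.7 or 0.8, no true effect, 20% dropout per arm. Dropout log-odds rise 0.5 per SD of the 9-month score in one arm only, which means about 31% dropout in the worst quarter and 11% in the best.

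- True response rate about 52% in both arms
- Complete-case RR 1.017, 1.027, 1.036; imputed from baseline and 9-month RMDQ, 1.00
- Same mechanism in both arms: RR 1.00, with each arm's rate 1 to 2 points too high
- SE(log RR) = √[2 × 0.48 / (0.52 × 567) × (1 + 62 × ICC)] = 0.073 at ICC 0.01 and 0.153 at ICC 0.10
- Bias in SE units: ln(1.036)/0.073 = 0.48 at most, ln(1.017)/0.153 = 0.11 at least

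**5. QALY bias under different handling.** Assumed: six visits with correlation 0.6, mean utility 0.70, SD 0.15, 0.20 or 0.25, and the same one-arm dropout rule applied to 9-month utility. Each dropout lacks only the 12-month value, whose area-under-the-curve weight is half of the last quarter-year, 0.125.

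| Handling | QALY difference (true value 0) |
|---|---|
| Complete cases | 0.010, 0.013, 0.017 |
| Area under visit-specific observed means | 0.001 to 0.002 |
| 9-month value carried forward | about −0.001 |
| Imputation from observed visits | 0.000 |
| Complete cases, same mechanism in both arms | 0.000 |

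At SD 0.15 the SE is 0.0093 (ICC 0.01) or 0.0197 (ICC 0.10), so the complete-case bias is 1.1 or 0.5 SE. The ratios are about the same at the other SDs. Almost all of that bias comes from discarding five observed utilities for each dropout, which the plan does not say it will do.

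**6. What the text supports.** The responder paragraph omits the time point, but Frequency and Duration of Follow-Up places the main comparison at 12 months, the primary model takes the RMDQ effect there, and the mediation analysis adopts 12 months for consistency with the primary outcome. The QALY sentence promises a value for all participants, so read literally it excludes no one and leaves only the method unstated.

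**The case for a change.** The strongest contrary case is that the plan was published precisely to limit analytic discretion, and a rule left open can be chosen after the data are seen. The choice can matter. With assumed response rates of 55% and 45%, complete cases give 0.55/0.45 = 1.22. Counting missing as failure, with 15% and 25% missing, gives (0.55 × 0.85)/(0.45 × 0.75) = 1.39; with 25% and 15% missing it gives (0.55 × 0.75)/(0.45 × 0.85) = 1.08. The existing safeguards are also partial. Item-level imputation does not help with a whole missed survey, the time offset serves the utilization models, and the record cross-check is made only when possible. A bivariate model that tolerates incomplete pairs would still need totals to be built. If dropout came earlier than month 9, more of each QALY would have to be filled than in step 5, and neither that case nor any bias in costs was computed.

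All of this stands as a description of missing detail. It does not show that a poor rule is planned. The large swings in the responder example come from treating missing as failure with unequal dropout, which nothing in the plan suggests. For covariates, allocation was disclosed only after baseline data were collected, so knowledge of arm is unlikely to have driven missing income or education, and no bias was shown. An intention-to-treat statement settles which arm people are analysed in; it does not conflict with an imputation method that has not been named.

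**Conclusion.** This is a gap that analysts can fill sensibly, and no change to the plan is needed. The primary analysis handles missing outcomes soundly and has its own sensitivity analysis for informative dropout. For the responder result, 12 months is the natural time point and the planned RMDQ imputation can be run with delta at zero. For the QALY, ordinary use of the observed visits removes nearly all of the illustrated bias. Standard missing-at-random methods exist for cost intervals and covariates.

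The size rests on assumed means, correlations, utilities and a one-arm dropout mechanism that nothing in the documents supports. Under those adverse assumptions, complete-case bias is 0.1 to 0.5 SE for the responder comparison and 0.5 to 1.1 SE for the QALY. The QALY figure falls to about 0.002 or less with simple use of observed data, and both are zero if dropout works alike in the two arms. The cost side was assessed only through completeness counts. None of this is shown to alter the trial's conclusions.
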